**Table 1. Geographical Distribution and Proportional Sample Allocation of Schools in Nablus**

Area	Total Schools	Proportion of Total	Sample Size (Proportional)
East	27	41.5%	6
Nablus			
Central	25	38.5%	6
Nablus			
West	13	20.0%	3
Nablus			
Total	65	100%	15

To ensure proportional representation, schools were evenly selected from three geographical areas of Nablus (East, Central, and West), corresponding to the number of schools in each area (Table 1). The Epi Info program was used to calculate the sample size based on schools with 9th-grade classes (East = 27, Central = 25, West = 13). A total of 15 schools were selected: 6 from East Nablus, 6 from Central Nablus, and 3 from West Nablus. The final sample included 10 governmental schools and 5 private schools, ensuring proportional distribution across the city.

Schools were eligible for inclusion if they had 9th-grade classes, were feasible for participation in the study and data collection and implemented an appropriate consent

process for students and their parents. According to the educational directorate's records for 2024, Nablus City had 2832 9th-grade students in governmental schools (males = 1360, females = 1472) and 737 students in private schools (males = 434, females = 303).

The G\*Power program was used to estimate the required sample size for the study, following the guidelines of Kang (2015, 2020). The effect size was set at  $dz = 0.5$ , with an alpha error probability ( $\alpha$ ) of 0.05 and a study power of 90% ( $1 - \beta$ ).

Based on these calculations, 536 students from intervention schools and 410 students from control schools were required to obtain accurate and meaningful data.

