### **Data Collection Processes**

The Al-Quds Committee for Ethical Considerations approved this study (REF.13/24). Consent forms were distributed to students, and their approval was sought before data collection began.

The researcher trained five dentists to conduct interviews and dental examinations, ensuring the data collection process was standardised and calibrated. Training sessions for the data collectors were held every 15 days throughout the research period to maintain consistency and accuracy in data collection.

During the baseline phase, all participants were provided with a comprehensive explanation of the study. Baseline data were collected in March 2024. The selected participants were randomly divided into intervention and control groups, ensuring that both groups were matched by age and gender. The control group received one oral educational session, while the intervention group participated in six sessions. The educational sessions were held every 10 days over two months.

After two months of interactive education, participants were re-examined and interviewed. Follow-up data were collected in the same schools using the same dental examination measures and questionnaires used during the baseline phase.

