**Table (2): Educational Sessions Program**

Session No.	Session Title	Duration & Group Size	Learning Objectives & Content	Teaching Methods	Instructional Tools	Evaluation Strategy
1	Anatomy & Physiology of the Oral Cavity and Clinical Presentation of Periodontal Disease	45–60 minutes, 30–35 participants	Objectives: Identify the major anatomical structures of the oral cavity; Explain the normal function of periodontal tissues Content: Overview of teeth, gingiva, periodontal ligament, alveolar bone; Signs and clinical presentation of periodontal disease (PD)	Interactive lecture & Q&A	Smartboard, photographs, PowerPoint, dental models	Prepare a brief report on a family member's oral condition
2	Prevention and Treatment of Periodontal Disease	45–60 minutes, 30–35 participants	Objectives: Describe primary preventive measures against PD; Compare non-surgical treatment options	Group discussion & live demonstration	Whiteboard & markers, photographs, PowerPoint	Compile a list of barriers to effective oral hygiene

			Content: Oral hygiene techniques: brushing, flossing, mouthwash; Professional measures: scaling, polishing, fluoride application		
3	Maintenance and Follow-Up of Preventive Measures	45–60 minutes, 30–35 participants	Objectives: Outline a maintenance schedule for periodontal health; Apply problem-solving strategies to common barriers  Content: Recall intervals and re-evaluation protocols; Strategies for overcoming patient-identified maintenance barriers	Brainstorming & group discussion	Photos, preventive devices (toothbrush, floss, mouthwash), posters, puzzles
4	Daily Preventive Practices	45–60 minutes, 30–35 participants	Objectives: Practice correct brushing and interproximal cleaning techniques;	Live demonstration under supervision	Whiteboard, PowerPoint, tooth models, preventive

			Reinforce daily oral-care routines	& mini-lecture	devices (brush, floss, mouthwash)
			Content: Live demonstrations of toothbrush and floss use; Hands-on practice with models and peer feedback		
5	Smoking and Its Harmful Effects on Periodontal Tissues	45–60 minutes, 30–35 participants	Objectives: Explain how tobacco smoking damages periodontal tissues; List short- and long-term oral health effects of smoking	Live demonstration on under supervision & lecture	Colorful PowerPoint slides with photos
			Content: Chemical effects of nicotine and tar; Epidemiology of PD in smokers vs. non-smokers		Compile a resource list on the oral-health impacts of smoking

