Statistical Analysis Plan (SAP)

Official Title: Effectiveness of an Interactive School-Based Oral Health Education Program in Reducing Periodontal Disease Among Palestinian Adolescents: A Double-Blind Intervention Study

NCT Number:

Document Date: March 1, 2024

Sponsor: Al-Quds University

Overview

This Statistical Analysis Plan outlines the statistical methods and procedures used to analyse data for the intervention study assessing the effect of a school-based oral health education program on periodontal conditions and related behaviours among 9th-grade students in Nablus City, Palestine.

Study Objectives

- Primary: To evaluate the effectiveness of the intervention on CPITN and S-OHI scores.
- Secondary: To assess changes in oral hygiene practices, dietary habits, and smoking behaviours.

Data Preparation and Management

Data were entered into IBM SPSS Statistics version 25.0.

All data were reviewed for completeness and consistency prior to analysis.

Normality testing was conducted using Shapiro-Wilk tests.

Missing data was minimal and handled by complete case analysis.

Statistical Analyses

Descriptive statistics will be used to summarise baseline characteristics by group (mean \pm SD, frequencies, percentages).

- Paired t-tests will be used to assess within-group differences from baseline to post-intervention.
- Independent t-tests were used to compare mean differences between the intervention and control groups.
- Statistical significance was set at $p < 0.05$.
- Confidence intervals were calculated at the 95% level for all primary outcomes.

Study Questions VS Analysis Plan

1. Can interactive educational sessions reduce **Community Periodontal Diseases Index** scores among 9th-grade students in Nablus City for two months?

1. Data Type and Variables

Dependent Variable: Community Periodontal Index for Treatment Needs (CPITN) **score** → Continuous quantitative variable

Independent Variable: Group type (Intervention vs. Control) → Binary categorical variable

Time Points: Pre-intervention (baseline)

Post-intervention (after two months) → true experimental design (pre-post measurements)

2. Statistical Design

Since there are two time points and two groups, the analysis includes:

A. Within-Group Analysis (Intervention group and control group):

Purpose: To assess whether there is a significant reduction in CPITN scores after the interactive educational sessions within the two groups themselves.

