Test to use: Paired t-test, as the data is normally distributed.

B. Between-Group Analysis (Post-intervention comparison):

Purpose: To compare the post-intervention CPITN scores between the intervention and control groups.

Test to use: Independent T-test as the data is normally distributed

Note: The two groups were examined for their differences in baseline measurement.

2. Can interactive educational sessions reduce **S-Oral hygiene index scores** among 9th-grade students in Nablus City within two months?

1. Data Type and Variables

Dependent Variable: Simplified Oral Hygiene Index (S-OHI) score → Continuous quantitative variable

Independent Variable: Group type (Intervention vs. Control) → Binary categorical variable

Time Points: Pre-intervention (baseline)

Post-intervention (after two months) → true experimental design

2. Statistical Design

Since there are two time points and two groups, the analysis includes:

A. Within-Group Analysis (Intervention group only):

Purpose: To assess whether there is a significant improvement (reduction) in S-OHI scores after the interactive educational sessions.

Test to use: *Paired t-test*, as the data is normally distributed.

B. Between-Group Analysis (Post-intervention comparison):

Purpose: To compare the post-intervention S-OHI scores between the intervention and control groups.

Test to use: *Independent t-test*, as the data is normally distributed

3. Will oral hygiene practices, smoking habits, and dietary habits improve among 9th-grade students after interactive educational sessions are applied in Nablus City?

Questionnaire responses related to oral hygiene practices, dietary habits, and smoking behaviour were **recoded** into scale variables to facilitate the computation of mean scores pre-and post-intervention. Correct answers reflecting preventive behaviours, in line with American Dental Association (2023) guidelines, were assigned the highest scores, while incorrect responses received the lowest scores, for example:

- "Do you clean your teeth?": Yes = 1, No = 0
- "How often do you clean your teeth?": Once/day = 1, Twice/day = 2, Three times/day = 3
- "How long does it take to clean your teeth?": One minute = 1, Two minutes = 2, More than two minutes = 3, Don't know = 0
- "Brushing technique": Scrubbing = 1, Bass = 2, Modified Bass = 3
- "Toothbrush type": Hard bristle = 1, Soft bristle = 2, Medium bristle = 3

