"Toothbrush replacement frequency": Every three months = 1, Two months = 2, Monthly = 3

Additional coding schemes are provided at the end of this document. The overall mean differences in oral hygiene practices, dietary habits, and smoking behaviour scores were then compared between groups using independent sample t-tests, with sub-analyses conducted for each behavioural domain separately. Statistical significance was set at $p < 0.05$.

1. Data Type and Variables

Dependent Variables (Behavioural Scores):

- **Oral hygiene practices score** → Continuous quantitative
- **Smoking habits score** → Continuous quantitative
- **Dietary habits score** → Continuous quantitative

Independent Variable: Group type (Intervention vs. Control) → Binary categorical

Time Points: Pre-intervention (baseline)

Post-intervention (after two months) → True experiment design (pre-post)

2. Statistical Design

Since the question involves **multiple behaviours** and **two time points**, the analysis will be conducted separately for each behavioural domain:

A. Within-Group Analysis (Intervention Group Only)

- **Purpose:** To evaluate if there was a significant improvement in each behaviour **after the intervention**.
- **Test to use:** Paired t-test for:
 - Oral hygiene practices score

- Dietary habits score
- Smoking habits score

(Assumes normal distribution)

B. Between-Group Analysis (Post-Intervention Comparison)

- **Purpose:** To compare post-intervention behavioural scores between intervention and control groups.
- **Test to use:**
 - **Independent t-test** for:
 - Oral hygiene practices
 - Dietary habits
 - Smoking behavior

(Assumes normal distribution)

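### The between-arm t-tests treat students as independent; if whole schools were allocated, as the sample-size text implies, p-values are too small and confidence intervals too narrow

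*SAP*

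**What the plan says.** **Analysis.** Under Statistical Analyses the SAP states: "Independent t-tests were used to compare mean differences between the intervention and control groups". The same test recurs for each study question. For CPITN the instruction is "Test to use: Independent T-test as the data is normally distributed", with the purpose "To compare the post-intervention CPITN scores between the intervention and control groups"; S-OHI is handled the same way. For question 3, the oral hygiene, diet and "smoking behaviour scores were then compared between groups using independent sample t-tests". For precision the SAP says: "Confidence intervals were calculated at the 95% level for all primary outcomes".

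**Design.** The protocol's sampling section draws 15 schools (6 East, 6 Central, 3 West). Below Table 1 it says that "536 students from intervention schools and 410 students from control schools were required". Data Collection Processes gives a different picture: "The selected participants were randomly divided into intervention and control groups", matched by age and gender. Table (2) has each session taught to "30–35 participants" at a time.

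Neither document mentions a school term, a cluster-robust standard error, a school ICC, a design effect or the number of schools per arm. The coefficients of 0.83 and 0.98 under Clinical Screening measure agreement between examiners, not similarity of students within a school.

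**The concern.** A school can be an intervention school or a control school only if it belongs to one arm, so the sample-size wording implies that schools were the units allocated. Students in one school share teachers, neighbourhood, family background and programme delivery, so their scores tend to be alike. The arm contrast then rests on 15 units rather than 946, while the independent t-test computes its standard error as if there were 946. A chance difference between a few schools could be reported as a programme effect on either primary outcome or any of the three behaviour scores. Recruiting more students from the same 15 schools would not cure this.

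Because the protocol also describes dividing participants, a reader cannot tell whether the planned test is valid.

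**Working it through.** **Inputs from the documents.** 536 intervention and 410 control students (total 946); 15 schools; significance level 0.05 (taken as two-sided, since the SAP does not say); session groups of 30–35.

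**Assumed, because not stated.** School ICC of 0.01, 0.05 or 0.10; a split of 8 v 7 or 10 v 5 schools; equal school sizes within an arm. The ICC is that of whichever quantity is analysed. The SAP is inconsistent on this: mean differences in its general section, post-intervention scores in questions 1 and 2.

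**The plan's own figure.** The stated inputs (dz = 0.5, α = 0.05, 90% power) give 44 pairs for a two-sided paired test. Read as a two-sample d of 0.5, they give 86 per arm. Neither gives 536 and 410, and no clustering inflation is stated that would. That is a separate problem and is not used below.

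**Step 1: design effect.** Average school size is 946/15 = 63.07. DE = 1 + (63.07 − 1) × ICC.

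**Step 2: variance ratio by split.** VR = (DE_i/536 + DE_c/410) / (1/536 + 1/410), where DE_i = 1 + (536/k_i − 1) × ICC, DE_c = 1 + (410/k_c − 1) × ICC, and k_i, k_c are the schools per arm. Example, 8 v 7 at ICC 0.05: DE_i = 1 + 66 × 0.05 = 4.30; DE_c = 1 + 57.57 × 0.05 = 3.88; VR = 4.06.

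**Step 3: true type I error of the nominal 5% test.** 2 × [1 − Φ(1.96/√VR)].

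**Step 4: 95% CI half-width.** As planned: 1.962 × √(1/536 + 1/410) = 0.129 SD. Allowing for clustering: t(13) = 2.160 times the clustered standard error, with 15 − 2 = 13 df.

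| ICC (assumed) | DE | VR, 8 v 7 | Type I, 8 v 7 | VR, 10 v 5 | Type I, 10 v 5 | CI half-width, 8 v 7 |
|---|---|---|---|---|---|---|
| 0.01 | 1.62 | 1.61 | 12.3% | 1.69 | 13.1% | 0.180 SD |
| 0.05 | 4.10 | 4.06 | 33.1% | 4.43 | 35.2% | 0.286 SD |
| 0.10 | 7.21 | 7.12 | 46.3% | 7.87 | 48.5% | 0.378 SD |

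Against 0.129 SD, the intervals are 1.4, 2.2 and 2.9 times wider.

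**Step 5: how small an ICC matters.** Type I error reaches 10% when DE = (1.96/1.645)² = 1.42, that is ICC = 0.42/62.07 = 0.007.

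**Step 6: simulation under school allocation** (8 v 7, 10,000 runs per ICC). The student-level t-test rejected a true null in 12.3%, 33.6% and 46.9% of runs; a t-test on school means did so in 4.8%, 5.0% and 5.1%.

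**Step 7: the other reading, students allocated within schools** (6,000 runs per setting). At school ICC 0, 0.01, 0.05 and 0.10 the t-test rejected in 4.9%, 5.1%, 4.8% and 4.2% of runs, so school effects alone cause no inflation. If session groups of 32.5 in the intervention arm also share an effect, with session-group ICC 0.01, 0.05 and 0.10, type I error is 6.6%, 13.1% and 20.3%. The control group size is not stated, so grouping was put in one arm only.

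**The case against.** The strongest reply is that the only sentence describing the act of allocation says participants were divided, and the school reading rests on one sample-size sentence. If students were divided within schools, the t-test is not inflated by school effects, as step 7 shows. This stands. The inflation is therefore conditional, and the defect certain from the documents is that the unit of allocation is contradictory. The sentence about dividing participants does not say it was done within schools, however, so it does not override the school wording.

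Second, the size depends on assumed values. The range of 12% to 49% is driven mainly by an ICC the documents do not give. Equal school sizes are assumed too (unequal sizes usually make matters worse), and the ICC of a change score need not match that of a raw score, because stable school differences cancel in a change. All true, but the direction holds for any positive ICC, and 0.007 is enough to double the error rate.

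Third, a large effect would survive. With 8 v 7 schools, an observed 0.5 SD difference gives t = 3.78 (p = 0.002) at ICC 0.05 and t = 2.86 (p = 0.014) at ICC 0.10, on 13 df. That is correct, so significance is at risk mainly for smaller effects; the planned intervals would be too narrow either way.

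Fourth, baseline adjustment is not needed to correct for clustering. Agreed; it is recommended because it uses data already collected and settles which quantity is analysed.

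**Conclusion.** The concern holds, as a conditional statement. If whole schools were allocated, every between-arm p-value in the SAP is too small, and the 95% intervals promised for CPITN and S-OHI are too narrow, for any positive school ICC. The figures in the table rest on the assumed ICCs, splits and equal school sizes. If students were allocated within schools, the planned test is sound unless session groups share an effect. Since the documents support both readings and the first would undermine both primary outcomes, this must be fixed before the results are interpreted. Confidence is high in the conditional statement; the documents do not establish which case applies.

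**What to change.** 1. Reconcile the protocol's sample-size text with Data Collection Processes: name the unit actually allocated and give the number of schools per arm.
2. **If schools were allocated:** for CPITN, S-OHI and each of the three behaviour scores, replace the independent t-test with a linear mixed model of the post-intervention score, adjusted for its baseline value, with a random intercept for school and Satterthwaite degrees of freedom. A t-test on the 15 school means is an acceptable alternative (13 df, or 11 if the three areas are in the model). Report the school ICC.
3. **If students were allocated within schools:** use the same baseline-adjusted model with school as a fixed stratum, plus a random effect for session group where it was recorded. If control students have no recorded groups, say so and apply that effect to the intervention arm only.

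**Cost.** SAP wording and a re-analysis, with no new data collection provided school and session-group identifiers were kept. The questionnaire description lists only type of school and school system, so this needs confirming; follow-up in the same schools suggests that school, at least, is known. Under school allocation the price is wider intervals and lower power. For an assumed between-arm difference of 0.5 SD on 13 df, before baseline adjustment, power is 93.7% (8 v 7) or 91.6% (10 v 5) at ICC 0.05, and 75.2% or 71.0% at ICC 0.10.

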### **Clinical Screening**

In this study, the Community Periodontal Index for Treatment Needs (CPITN) was used to assess the prevalence of periodontal disease (PD) among 9th-grade students before and after the intervention. For adolescents, CPITN scores 0, 1, and 2 are used to assess gingivitis:

- Score 0: Healthy gingiva
- Score 1: Gingival bleeding observed after gentle probing
- Score 2: Presence of supra or sub-gingival calculus

For adults, CPITN includes the following scores for periodontitis:

- Score 3: Pathological pockets measuring 4 to 5.99 mm deep

Score 4: Pathological pockets measuring 6 mm or deeper

Each sextant of the mouth examined was assigned a code number, with the index teeth representing each sextant: 16, 11, 26, 36, 31, and 46 (22).

The Oral Hygiene Index-Simplified (OHI-S) was used to determine the oral hygiene status of the subjects. This index consists of two components: debris and calculus, each with a possible score range of 0 to 3. The amounts of calculus and debris were assessed by examining the facial surfaces of teeth numbers 11, 16, 26, and 31 and the lingual surfaces of teeth 36 and 46. The scores for calculus and debris were added together and divided by the number of examined surfaces to calculate the OHI-S score for each individual.

In the pilot phase of the study, the Interclass Correlation Coefficient (ICC) was calculated to assess the reliability of the clinical measurements. A total of 20 students were examined five times by five data collectors, resulting in ICC values of 0.83 for CPITN and 0.98 for OHI-S, indicating high reliability.

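### The SAP never says how six ordinal CPITN sextant codes become one student value, and that choice can decide whether this primary outcome shows a benefit or no effect

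*SAP*

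**What the plan says.** The Protocol, Clinical Screening, sets the scale: "For adolescents, CPITN scores 0, 1, and 2 are used to assess gingivitis", meaning healthy gingiva, bleeding on probing and calculus. It sets the unit of recording: "Each sextant of the mouth examined was assigned a code number, with the index teeth representing each sextant". It also states the purpose: CPITN "was used to assess the prevalence of periodontal disease (PD) among 9th-grade students before and after the intervention". For OHI-S, the same section gives a formula that leads from surfaces to one score per student. CPITN has no such formula.

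The SAP, study question 1, lists the CPITN score as a "Continuous quantitative variable". The within-group test, in both arms, is "Test to use: Paired t-test, as the data is normally distributed". The between-group test is an independent t-test on post-intervention scores, with the same justification. Under Data Preparation and Management the SAP adds: "Normality testing was conducted using Shapiro-Wilk tests". It names no alternative test. Appendix A recodes questionnaire items only and does not cover CPITN.

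**The concern.** CPITN is one of two primary outcomes, yet the variable to be tested is not defined. At least four student-level summaries fit the text: the mean of six codes, the worst code, the number of affected sextants, and presence or absence of disease. They answer different questions and respond differently to the same clinical change. If the choice is left open until the data are seen, a reader cannot tell whether the reported result was the planned one.

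A fall in a mean code also counts a step from calculus to bleeding as equal to a step from bleeding to healthy. It does not say how many students became free of disease, which is what the Protocol's reference to prevalence leads a reader to expect.

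**Working it through.** **Inputs from the documents.** Codes 0/1/2, six sextants per student (Protocol, Clinical Screening); 536 intervention and 410 control students (Protocol, Sample techniques and process); significance at 0.05 (SAP, taken as two-sided). The documents give no CPITN distribution, SD or expected difference, so there is no CPITN figure of the plan's own to reproduce.

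**Step 1: one mouth, no assumed rates.** Baseline 1,1,1,1,1,1; follow-up 2,0,0,0,0,0.

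| Summary | Baseline | Follow-up | Reading |
|---|---|---|---|
| Mean code | 6/6 = 1.00 | 2/6 = 0.33 | better |
| Sextants with code 1 or higher | 6 | 1 | better |
| Any sextant with code 1 or higher | yes | yes | unchanged |
| Worst code | 1 | 2 | worse |
| Sextants with code 2 | 0 | 1 | worse |

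The summaries are not interchangeable.

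**Step 2: trial level.** Assumptions: sextant code shares 30/40/30%, latent within-student correlation 0.5, calculus unchanged, a given share of bleeding sextants cleared in the intervention arm, no school effect, independent t-tests, 1,500 replicates.

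| Bleeding cleared | Mean code | Worst code | Affected sextants | Any-sextant prevalence |
|---|---|---|---|---|
| 30% | 89% | 11% | about 100% | 39% |
| 20% | 57% | 7% | 98% | 17% |

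At 30% clearance the mean code was significant and the worst code was not in 79% of trials.

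**Step 3: check by formula.** The standardised differences at 30% clearance were d = 0.21 (mean code) and 0.05 (worst code). The standard error of d is about sqrt(1/536 + 1/410) = 0.0656.
- Mean code: 0.21/0.0656 = 3.20; power about Φ(3.20 − 1.96) = Φ(1.24) = 89%.
- Worst code: 0.05/0.0656 = 0.76; power about Φ(0.76 − 1.96) + Φ(−0.76 − 1.96) = 11.5% + 0.3% = 12%.

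Both agree with the simulation.

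**Step 4: sensitivity.** Across three assumed code distributions, at 30% clearance, power was 86-98% for the mean code and 9-35% for the worst code. A differently built model, with calculus in 20% of sextants in both arms and bleeding propensity 50% v 40%, gave a significant benefit in 72% of trials by mean code, 97% by affected sextants and 13% by worst code.

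**Step 5: normality.** Shapiro-Wilk at n = 410 rejected in all 200 simulated samples, for mean code and for worst code. With no true effect, however, the t-test rejected in 4.4-6.7% of trials across separate runs, close to the nominal 5%.

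**The case against.** - **The SAP's wording leans towards a mean.** It speaks of a continuous score and of mean differences, and neither document mentions a worst code. A six-sextant mean has 13 possible values (sums 0 to 12), so the ordinal objection is weaker for it. This narrows the ambiguity but does not remove it: the mean is never stated, and the Protocol's reference to prevalence points to a proportion.
- **The power figures rest on assumptions.** This stands. Under 30/40/30 about two-thirds of students have calculus somewhere, and calculus was held fixed, so the worst code can hardly move. The figures show that the choice can matter, not how much it did here.
- **A reader might infer that the same data would give opposite conclusions.** The documents do not support that as a trial-level claim. The one-mouth example moves in both directions, but significant benefit by mean code together with significant harm by worst code occurred in 0 to 2.3% of simulated trials. Frequent reversal needed a calculus count as the summary and an assumed rise in calculus in the intervention arm.
- **A reader might infer that non-normality invalidates the t-tests.** It does not at 536 and 410 (step 5). The paired test also concerns within-student differences, not the codes themselves, and the SAP does not make the choice of test conditional on Shapiro-Wilk.
- **Counting affected sextants has its own blind spot.** It merges bleeding and calculus. With assumed calculus of 15% in control and 20% in intervention, and bleeding propensity 50% v 30%, that count showed benefit in 100% of trials while the calculus count showed significant harm in 89%. This stands, and is why code 2 must be reported separately.

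**Conclusion.** The point holds. A primary outcome lacks a student-level definition, its stated purpose (prevalence) has no matching analysis, and the reason given for the test is not credible for codes of this kind. The consequence is benefit versus no effect: about 86-98% against 9-35% power in the illustrative case. This is conditional on assumed code distributions, 30% clearance of bleeding sextants, unchanged calculus and no school clustering. The weight lies on the missing summary rule. The normality statement is a fault of justification with little effect on error rates in unclustered data, and the simulations say nothing about error rates when students are clustered in schools.

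**What to change.** In the SAP, study question 1:

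1. Describe CPITN as ordinal and name one student-level summary, for example the number of examined sextants with code 1 or higher, or the six-sextant mean. Fix it before the arms are compared. Parts of the SAP are in the past tense, so if the comparison has already been made, label the choice post hoc.
2. Compare arms at follow-up with a model suited to that summary, adjusted for the student's baseline value and with a school random effect. For the count this could be a binomial mixed model out of sextants examined. It would also need a student-level random effect or overdispersion term, because sextants in one mouth are correlated.
3. Report by arm, with risk difference and 95% CI, the prevalence of any sextant with code 1 or higher and, separately, of any sextant with code 2, so that worsening calculus is not hidden.
4. Delete normality as the reason for the test. If the count is chosen, the mean code can stay as a supportive analysis.

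The cost is SAP wording and slightly more analysis of codes already recorded. If the count is used, its effect measure is less familiar than a mean difference.
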